### Randomization

Randomization takes place at baseline after informed consent is given. The randomization is done in varying blocks of 6-8, stratified by sex and age group (65-74; 75+) using REDCap

electronic data capture tools hosted at the Region of Southern Denmark. As described above, participants are randomized to one of the four groups and given the allocated treatment.

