## 3.0 STUDY METHODS

### Trial design

A single-blinded, placebo controlled randomized clinical trial. Participants are randomized 1:1 to BCG or placebo and will be followed for 12 months post-randomization with respect to illness, medical contacts, use of antibiotics, hospitalization, and death. The follow-up takes place both through self-reporting and through the Danish National Registers. The participants will receive an electronic questionnaire biweekly with questions about illness, medical contacts, other vaccinations, and side effects.

People  $\geq 65$  years of age are eligible for participation.

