### **Randomization**

Randomization takes place at baseline after informed consent is given. The randomization is done in varying blocks of 6-8, stratified by sex and age group (65-74; 75+) using REDCap electronic data capture tools hosted at the Region of Southern Denmark.

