## 10.0 STUDY METHODS

### Trial design

A single-blinded, placebo controlled, randomized clinical trial, with nested immunological studies. Participants are randomized 1:1:1:1 to four groups: BCG 14 days before, together with, or 14 days after IIV compared to placebo.

People  $\geq 65$  years of age who plan to accept the offer of seasonal influenza vaccination are eligible for participation.

Participants are vaccinated once at day 0 and twice at day 14 (one shot in each arm). All participants receive the standard seasonal IIV recommended by the Danish Board of Health. The participants will come back for a follow-up interview at day 42 and all are followed for six months post-randomization with electronic questionnaires about their health. These include information on symptoms and disease, potential side effects, other vaccinations, visits to general practitioner or on call doctor, and hospitalizations. Every survey period is 14 days, starting from day 0 (inclusion).

Blood samples for influenza antibody testing are collected from all participants at day 14 and 42. Samples for further immunological analyses are collected from subgroups at day 0, day 14, day 21, and day 42.

Vaccination schedule:

Group	Day 0 (one shot)	Day 14 (two shots)	Day 42
1	BCG	IIV + Placebo	Follow up visit
2 (Control)	Placebo	IIV + Placebo	Follow up visit
3	Placebo	IIV + BCG	Follow up visit
4	IIV	Placebo + BCG	Follow up visit

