### **Sample size**

We aim to include 75 participants in each group, 300 in total. With an anticipated seroconversion rate of 50% in the control group, we should be able to show a 30% increase in seroconversion rate associated with BCG vaccine with 80% power and an alpha of 0.05, anticipating 10% loss to follow-up.

All participants are followed for clinical symptoms for six months. With this sample size, we will only be able to show differences in clinical symptoms if such differences are pronounced.

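### Part B describes 1:1:1:1 allocation in varying blocks of 6 to 8, but only a block of 8 can hold four equal groups, so the stated block sizes need correcting

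*SAP*

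**What the plan says.** Part B, section 10.0, Trial design: "Participants are randomized 1:1:1:1 to four groups: BCG 14 days before, together with, or 14 days after IIV compared to placebo".

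Part B, section 10.0, Randomization: "The randomization is done in varying blocks of 6-8, stratified by sex and age group (65-74; 75+) using REDCap". The same paragraph ties these blocks to the four-way allocation: "As described above, participants are randomized to one of the four groups and given the allocated treatment".

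Part B, section 10.0, Sample size: "We aim to include 75 participants in each group, 300 in total".

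Part A, section 3.0, has the same block sentence word for word, but there the allocation is two-way: "Participants are randomized 1:1 to BCG or placebo".

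On adjustment, Part B section 14.0 puts age group and sex into both primary models (change in titre and seroconversion). Under Secondary outcomes it states that adjustment only for the association between day-42 titre and later infection. For the comparison of infections between randomized groups it states none. For the immunological outcomes the only adjustment named is for the response in the control condition.

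**The concern.** A permuted block keeps groups equal only if its size is a multiple of the number of groups. The Part B block sizes therefore conflict with the Part B ratio, and the SAP contains nothing that reconciles them: no unequal blocks, no two-step randomization, no separate list of sizes. A reader cannot tell whether the list used other sizes, used only 8, or included blocks of 6 that were unequal by construction. As it stands, the sentence would pass into the trial report as a randomization method that does not agree with its own ratio.

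A smaller point follows from the stratification. Sex and age group are the stratification factors, and stratified blocks are meant to balance them across groups. The group comparisons in section 14.0 that do not adjust for these factors rely entirely on that balance, and they do not use the factors to gain precision.

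**Working it through.** **Inputs.** Part B: four groups, 1:1:1:1, block sizes 6 to 8, four strata (sex by two age groups), 75 per group and 300 in total (section 10.0). Part A: two groups, 1:1, the same block sizes (section 3.0).

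**Divisibility.** Participants per group in a balanced block = block size / number of groups, which must be a whole number.

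| Block size | Part A (2 groups) | Part B (4 groups) |
|---|---|---|
| 6 | 6/2 = 3, fits | 6/4 = 1.5, does not fit |
| 7 | 7/2 = 3.5, does not fit | 7/4 = 1.75, does not fit |
| 8 | 8/2 = 4, fits | 8/4 = 2, fits |

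Read as sizes 6 and 8, the sentence works for Part A. For Part B only 8 qualifies, and one size is not a varying size. Varying balanced blocks for four groups would need sizes such as 4 and 8, or 8 and 12.

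**What blocks of 6 would have done.** The nearest to balance in a block of 6 is 2:2:1:1. This was simulated under assumptions that are not in the SAP: four strata of 75, sizes 6 and 8 equally likely, the two extra places in each block of 6 given to two different groups at random, and 1,500 runs. The comparison used blocks of 4 and 8.

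| Blocks | Mean group size | Mean gap, largest minus smallest | 95th percentile of gap |
|---|---|---|---|
| 6 and 8, extras at random | about 75 | 5.9 | 11 |
| 4 and 8 | about 75 | 2.4 | 4 |

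**What such a gap costs.** For two groups of 75 + d/2 and 75 − d/2, the equal group size with the same precision is 75 × [1 − ((d/2)/75)²].

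- d = 6: 75 × [1 − (3/75)²] = 75 × 0.9984 = 74.9 per group.
- d = 11: 75 × [1 − (5.5/75)²] = 75 × 0.9946 = 74.6 per group.

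The loss of precision is about 0.2% and 0.5%. This is negligible.

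**The case against.** The strongest reply is that this is a slip of wording with no consequence for the analysis. Most of that stands. The identical Part A sentence makes a carried-over text the likeliest cause, and no estimand, model or test in Part B depends on the block sizes. What does not stand is leaving the sentence alone: the SAP chose to state the block sizes, and what it states cannot be squared with its own ratio.

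Some stronger readings are tempting, and the document does not support them.

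- *The randomization cannot have been carried out.* A list with unequal blocks of 6, filled at random, is feasible and gives 1:1:1:1 in expectation. The SAP describes no such list, but it does not exclude one.
- *Two groups ended up well short.* If the same two groups always took the extra places and half the blocks were of size 6, the ratio would be 4:4:3:3 (2:2:1:1 plus 2:2:2:2). Among 300 participants that is about 300 × 4/14 = 86 against 300 × 3/14 = 64, a gap of about 21. The SAP supports neither assumption.
- *Allocation drifted with calendar time.* Even a fixed 4:4:3:3 ratio is constant over enrolment and so is not confounded with date. Drift would require the mix of block sizes to change during recruitment, and nothing suggests that.
- *Staff could predict allocations.* A fixed block of 8 would be easier to guess than varying blocks. The SAP does not say that only 8 was used, or that staff knew the block sizes.

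On the adjustment, one could point to the sentence in section 14.0, Methods, that analyses are also stratified by sex and age group. It reads as separate results by subgroup beside the pooled analysis. It does not say that the pooled models are adjusted, and the explicit adjustment in the primary models suggests that adjustment is stated where it is meant.

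**Conclusion.** The point holds as an error in the stated randomization method for Part B. That rests on divisibility alone and on no assumption. It is minor: it does not put the validity of the randomization or the planned primary analysis in doubt. If blocks of 6 were used and filled at random, the expected effect is a gap of about 6 participants between the largest and smallest group, against about 2 with blocks of 4 and 8. Those figures depend on the simulation's assumed equal strata and equal mix of block sizes. Which sizes were used cannot be settled from the SAP.

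Adding the stratification factors to the remaining group comparisons is a low-cost improvement that brings them into line with the primary models. It does not remedy a demonstrated imbalance.

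**What to change.** 1. Check the REDCap allocation table for Part B and correct section 10.0, Randomization, to the block sizes actually used.
2. If any block was not a multiple of 4, say so, state how the extra places were assigned, and report realised group sizes in each sex-by-age stratum. The 1:1:1:1 statement can remain if unequal blocks were filled at random.
3. In section 14.0, Secondary outcomes, add sex and age group to the models comparing randomized groups on self-reported infections and on the immunological outcomes. The primary models need no change.

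No covariate for enrolment period is needed.

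The cost is one look-up, one corrected sentence and two binary covariates. In the trained-immunity subset of 15 per group (60 in all), a model at a single time point would keep 60 − 4 − 2 = 54 residual degrees of freedom. In the lymphocyte subset, if 10 from each of groups 1 to 3 is meant, it would keep 30 − 3 − 2 = 25.

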### **Sample size**

We aim to include 75 participants in each group, 300 in total. With an anticipated seroconversion rate of 50% in the control group, we should be able to show a 30% increase in seroconversion rate associated with BCG vaccine with 80% power and an alpha of 0.05, anticipating 10% loss to follow-up.

All participants are followed for clinical symptoms for six months. With this sample size, we will only be able to show differences in clinical symptoms if such differences are pronounced.

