### **Sample size**

With an expected incidence of “acute infection” of 20% we will be able to show a 25% reduction in the risk of acute infection in the intervention group compared to the placebo group by including a total of 1890 individuals: 945 individuals in each group. Since the primary outcome data to a large extent are obtained via national registers, we anticipate limited loss of power due to loss to follow-up. We therefore aimed to enroll 1900 participants.

Due to the pandemic and varying infectious disease precautions, recruitment took longer than anticipated, and we ended up recruiting a total of 1706 participants (90% of the anticipated sample size) between September 2020 and December 2021.

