### Objectives and hypothesis

We will test the effects of BCG vaccination on the specific immune response to IIV and on the immune system and health in general in people  $\geq 65$  years, with the aim to:

- Improve their specific antibody response to influenza vaccination.
- Improve their general resistance towards infections.
- Study the effect of BCG on classical lymphocyte-dependent responses, and the induction of innate immune memory.

We will test the following hypotheses:

- a) BCG vaccine given two weeks prior to, together with, or two weeks after IIV is associated with a 30% increase in seroconversion to IIV and/or a significant increase in influenza antibody titers.
- b) The hypothesized potentiating effects of BCG is due to a combination of classical lymphocyte-dependent responses, and the induction of innate immune memory (trained

immunity) in myeloid cells.

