## **11.0 STATISTICAL PRINCIPLES**

### **Levels of confidence and p-values**

A double-sided p-value of  $< 0.05$  will be considered statistically significant. 95% confidence intervals will be provided.

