#### Primary outcome:

Mean change in GMT in samples from day 14 and 42 will be compared between the control group and the three treatment groups in linear regression analyses with adjustment for baseline level of GMT, age group, and sex. In case residuals are not normally distributed, the analysis will be performed on log-10 transformed change in GMT instead. The proportion of participants who seroconvert will be compared in logistic regression analysis with adjustment for age group and sex.

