**Table 2: Results primary outcome.**

Change in antibody levels to influenza virus strains included in the IIV, comparing levels at day 14 and day 42.

[figure not shown]
Influenza strain	Change in antibody titer from day 14 to day 42, mean (sd) $\beta$ (95% CI)			
	Group 1	Group 2 (Control)	Group 3	Group 4
A/Victoria	xx (xx-xx) xx (xx-xx)	xx (xx) (ref.)	xx (xx) xx (xx-xx)	xx (xx) xx (xx-xx)
A/Cambodia	xx (xx) xx (xx-xx)	xx (xx) (ref.)	xx (xx) xx (xx-xx)	xx (xx) xx (xx-xx)
B/Washington	xx (xx) xx (xx-xx)	xx (xx) (ref.)	xx (xx) xx (xx-xx)	xx (xx) xx (xx-xx)
B/Phuket	xx (xx) xx (xx-xx)	xx (xx) (ref.)	xx (xx) xx (xx-xx)	xx (xx) xx (xx-xx)
	Seroconversion N (%) OR (95% CI)			
A/Victoria	xx (%) x.xx(x.xx-x.xx)	xx (%) (ref.)	xx (%) x.xx (x.xx-x.xx)	xx (%) x.xx (x.xx-x.xx)
A/Cambodia	xx (%) x.xx(x.xx-x.xx)	xx (%) (ref.)	xx (%) x.xx (x.xx-x.xx)	xx (%) x.xx (x.xx-x.xx)
B/Washington	xx (%) x.xx(x.xx-x.xx)	xx (%) (ref.)	xx (%) x.xx (x.xx-x.xx)	xx (%) x.xx (x.xx-x.xx)
B/Phuket	xx (%) x.xx(x.xx-x.xx)	xx (%) (ref.)	xx (%) x.xx (x.xx-x.xx)	xx (%) x.xx (x.xx-x.xx)

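### Part B's stated 80% power for a 30% rise in seroconversion does not follow from its inputs: power is about 42% if the rise is relative and about 96% if it is absolute

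*SAP*

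**What the plan says.** Part B, section 10.0, Sample size: "We aim to include 75 participants in each group, 300 in total". Controls are expected to seroconvert at 50%, and a tenth of participants are expected to be lost. On that basis the section claims: "we should be able to show a 30% increase in seroconversion rate associated with BCG vaccine with 80% power and an alpha of 0.05".

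Part B, section 2.0, Objectives and hypothesis, repeats the effect: BCG given before, with or after influenza vaccine "is associated with a 30% increase in seroconversion to IIV". Neither place gives the target rate in the BCG groups or says whether 30% is relative or in percentage points.

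Part B, section 11.0, sets a two-sided 0.05 threshold. Section 14.0 describes the analysis: "The proportion of participants who seroconvert will be compared in logistic regression analysis with adjustment for age group and sex". It mentions no multiplicity correction. Shell Table 2 shows each of the three BCG groups against Group 2 for each of four strains, which makes 12 seroconversion contrasts.

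**The concern.** The control rate, group size, loss, alpha and power are all stated, so the implied target rate can be worked out. It matches neither meaning of a 30% increase.

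The scale decides what a null result can rule out. Suppose 67 per group are evaluable and both groups seroconvert at 50%. The 95% confidence interval for the difference is then about ±17 percentage points, which excludes a true rate of 80% but not one of 65%. If the relative effect was meant, a null finding would be reported against a claimed 80% power when the real figure was about 42%. If the absolute effect was meant, either the power is understated or the size rests on a stricter alpha than the one the analysis uses.

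**Working it through.** **Inputs.** Control rate p1 = 0.50, 75 per group and 10% loss (section 10.0), so 75 × 0.9 = 67.5 evaluable, taken as 67 or 68. Two-sided 0.05 (section 11.0). One BCG group versus control (section 14.0 and Table 2).

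**Formulas** (two proportions, pooled variance under the null, m = mean of p1 and p2, d = p2 − p1):

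- n = [z_a √(2m(1−m)) + 0.8416 √(p1(1−p1) + p2(1−p2))]² / d²
- power = Φ{[d√n − z_a √(2m(1−m))] / √(p1(1−p1) + p2(1−p2))}
- continuity-corrected n = (n/4)[1 + √(1 + 4/(nd))]²

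**Relative, 0.50 vs 0.65.** m = 0.575; the two terms are 1.96 × 0.6991 = 1.3702 and 0.8416 × 0.6910 = 0.5816.

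- n = (1.9518)² / 0.0225 = 169.3 evaluable per group (182.4 with correction).
- Power at 67: (0.15 × 8.185 − 1.3702) / 0.6910 = −0.206, so 41.8%.

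**Absolute, 0.50 vs 0.80.** m = 0.65; the two terms are 1.96 × 0.6745 = 1.3221 and 0.8416 × 0.6403 = 0.5389.

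- n = (1.8610)² / 0.09 = 38.5 evaluable per group (44.9 with correction).
- Power at 67: (0.30 × 8.185 − 1.3221) / 0.6403 = 1.770, so 96.2%.

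| Comparison | Alpha (two-sided) | Power, n = 67 | Power, n = 68 |
|---|---|---|---|
| 50% vs 65% | 0.05 | 41.8% | 42.4% |
| 50% vs 80% | 0.05 | 96.2% | 96.4% |
| 50% vs 65% | 0.05/12 | 13.1% | 13.4% |
| 50% vs 80% | 0.05/12 | 79.3% | 80.1% |

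**Randomised per group for 80% power at 0.05.** Relative: 170/0.9, rounded up to 189 (204 with continuity correction). Absolute: 39/0.9, rounded up to 44 (50 with correction). Neither is 75.

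**Other variants at alpha 0.05** (relative; absolute):

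- no loss, n = 75: 46%; 98%
- continuity correction: 35–36%; 94–95%
- Fisher exact: 34–35%; 95%
- one-sided: 54–55%; 98%
- three BCG groups pooled against control: 59%; over 99%
- pooled and one-sided: 70–71%, or 74% with no loss; over 99%

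A 30% rise in the odds, as a literal reading on the logistic scale, gives about 11%. No variant gives 80%.

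**Effect that does match.** With 67 per group, 80% power at 0.05 corresponds to 50% versus 73.3% (74.7% with continuity correction). That is about 23 points, or about 47% in relative terms.

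**Settings that come near 75 per group.** For the absolute effect at 0.05/12 (3 contrasts × 4 strains), n = 67.9 evaluable, and 67.9/0.9 = 75.4 randomised. The absolute effect at 0.05/6 with continuity correction also gives 75, although Table 2 shows no obvious family of six tests.

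**Usage in Part A.** Section 3.0 of Part A says "we will be able to show a 25% reduction in the risk of acute infection in the intervention group", from an expected 20%. A fall of 25 points from 20% is impossible, so this is relative: 20% to 15%. With two-sided 0.05 and an assumed 80% power (Part A states none), n = (1.5045)² / 0.0025 = 905.4, or 944.9 with continuity correction. That is the stated 945 per group.

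**Interval under a null result.** 1.96 × √(2 × 0.25/67) = 0.169.

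**The case against.** The strongest defence is that the plan meant 50% to 80% and that 0.05 was a family-wise level shared over the 12 seroconversion tests. The absolute scale, 10% loss, 75 per group and 80% power then fit almost exactly, and the gap would be a missing multiplicity rule, not wrong arithmetic. This is plausible and worth asking the sponsor. It does not rescue the text: section 10.0 gives alpha as 0.05 with no division, and section 11.0 says a two-sided p-value below 0.05 "will be considered statistically significant. 95% confidence intervals will be provided". Section 14.0 adds no correction. If the size was built that way, the analysis does not match it.

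A second point is that on the absolute reading at 0.05 the claim holds as a minimum, because 96% exceeds 80%. That is fair: there is no shortfall on that reading, only a figure that the inputs do not produce. But the plan never says the rise is absolute, and Part A's usage points the other way.

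Third, the sample-size text names no contrast. Pooling the BCG groups raises the relative figure only to 59%, and the planned analysis is group by group.

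Fourth, seroconversion is not the only primary measure. Titre change is listed too, the hypothesis can be met by either, and confidence intervals will be shown throughout. This limits the damage, and the estimates stay valid, but the stated power is still wrong for the comparison it describes.

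**Conclusion.** The concern holds. At the stated two-sided 0.05, with 67 to 68 evaluable per group, power is about 42% for a relative 30% increase and about 96% for an absolute one. The plan's 80% follows from neither. On the relative reading the type II risk is about 58% instead of 20%, and 80% power would need about 189 randomised per group. That the relative reading was intended is an inference from Part A, not something Part B states.

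The figures assume each BCG group is compared with control and use unadjusted two-proportion formulas. The planned logistic model adjusts for age group and sex, and the SAP gives no inputs for that. To reach 80% on the relative reading, adjustment would have to be worth about 2.5 times the sample (169/67.5), and nothing in the plan supports such a gain.

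This should be fixed. It does not invalidate the planned estimates.

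**What to change.** In Part B, Objectives and hypothesis and Sample size, state both seroconversion rates, whether 30% is relative or absolute, the contrast (each BCG group versus control) and the alpha per test. The scale should be the one used when the trial was sized, not one chosen once results are known. Then restate the power, for example:

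> With about 67 evaluable participants per group, each BCG group versus control has 80% power (two-sided 0.05 per test, unadjusted) to detect 50% versus about 73% seroconversion (about 75% with continuity correction). Power is about 42% for 50% versus 65% and about 96% for 50% versus 80%.

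If the size was built on a multiplicity-adjusted alpha, give that alpha in the sample-size section and apply the same correction in sections 11.0 and 14.0. Otherwise describe 0.05 as a per-test level.

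The cost is SAP wording, with no extra participants and no change to the planned estimates. On the relative reading the stated power becomes much less favourable. If a corrected alpha was intended, applying it makes each seroconversion test stricter.

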### **Timing of final analyses and outcome assessments**

All outcomes are analyzed after end of trial.

## **11.0 STATISTICAL PRINCIPLES**

### **Levels of confidence and p-values**

A double-sided p-value of  $< 0.05$  will be considered statistically significant. 95% confidence intervals will be provided.

### **Protocol violations**

Protocol deviations and exclusions will be reported for each treatment arm.

## **12.0 STUDY POPULATION**

### **Screening data**

As described for part A.

### **Recruitment**

As described for part A.

### **Exclusion/lost to follow-up**

Participants who are excluded after randomization or lost to follow up are not replaced.

Participants are under follow-up for six months post-randomization or until they withdraw their consent, migrate to another country, or die.

### **Baseline characteristics, study population**

Continuous baseline characteristics will be reported as mean and standard deviation or median and inter-quartile range, as appropriate. Categorical baseline characteristics will be reported as count and percentage. No statistical testing for baseline characteristics will be performed.

